### 2.0 Background

2.1 Significance: VLBW preterm infants commonly experience growth failure, most significantly in length and FFM, during their first weeks of life while they are sick and dependent on parenteral nutrition. This growth failure is occurring at a critical time in brain development and has been shown to have a lasting negative impact on their neurodevelopment The majority of these infants do not recover from this early growth failure has been shown by our group to persist even beyond 2 years CA. In addition to the neurodevelopmental consequences, early growth failure also increases these infants risk of developing later

hypertension, insulin resistance, obesity and other components of metabolic syndrome, by necessitating later rapid catch-up growth in infancy and toddlerhood.

There are several factors contributing to this early growth failure, and many (e.g. illness and inflammation) of them remain largely out of our control. In contrast, nutrition is a factor the health care team can control, and early enhancements in nutrient provision may be our opportunity to prevent the above described early growth failure, improve neurodevelopment and optimize the later metabolic health of VLBW preterm infants. Multiple small retrospective studies have found significant decreases in growth failure (defined as weight z-score <10th percentile at discharge) after a slight change in their NICU parenteral nutrition protocol. In addition, multiple groups have reported improved neurodevelopmental outcomes, including improved language scores, increased developmental quotient and decreased incidence of brain lesions on MRI in infants receiving more aggressive parenteral nutrition in the first weeks of life. Specifically, Stephens et al reported an increase of 4.6 points in the Mental Developmental Index (MDI) at 18 months for every additional 10 kcal/kg/day of energy provided in the first week of life and an 8.2 point increase in the MDI for every additional gram/kg/day of protein provided in the first week $^{18}$ .

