Despite the potential benefits, early enhanced macronutrient provision to VLBW preterm infants is not routinely practiced due to concerns about intolerance and toxicity. These concerns are based on older trials using different nutritional products than those routinely used in NICU's today. More recent studies (mostly small and retrospective) have found that earlier introduction and more rapid advancement of lipids and protein are safe, and in fact may decrease the incidence of hyperglycemia and parenteral nutrition associated cholestasis. In addition, recent findings of increased adiposity among preterm infants at term CA has discouraged early enhanced nutrient provision based on a fear that this strategy, while being beneficial for the brain, will nonetheless lead to further increases in adiposity. However, our group and others have instead found that increased nutrition provision, both in calories and in protein, leads to increased FFM gains, without accompanying increases in FM or adiposity7.19. Work under Specific Aims 1 and 2 will address this uncertainty through a comprehensive examination of both neurodevelopmental and metabolic outcomes (i.e., body composition) in a randomized nutrition intervention trial.

> While the relationships between early malnutrition, poor growth and worsened neurodevelopment are relatively clear, the mechanisms behind these associations have vet to be elucidated. IGF-I is nutritionally regulated and negatively influenced by early malnutrition. Levels of IGF-1 play an important role in early postnatal growth, body composition and blood pressure in childhood, and improved neurodevelopmental outcomes among preterm infants. Circulating growth factor concentrations, like IGF-1, are therefore potential mediators of the effect of nutrition intervention on diverse preterm outcomes, which hypothesis we are testing in Specific Aim 3. If this hypothesis is supported, IGF-1 could then be used as a biomarker for prediction of later outcomes and, relatedly, as a tool for monitoring the success of early nutrition interventions. In the future, development of a nutritional intervention that optimizes IGF-1 levels early in life for preterm infants could indicate whether or not the proper balance is being struck between adequate early FFM gains to optimize neurodevelopment and minimizing excess FM gains to decrease long-term metabolic risk.

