#### 16.0 Data Management

15.1 Data Analysis Plan: Data from the various domains will be entered by the study personnel into a web-based secure database (RedCap) for storage, retrieval and analysis. The NICU dietician is responsible for abstracting nutritional data from the electronic medical record (Epic). ADP data will be entered into the database by the study coordinators. ERP data will be abstracted by [name] and cleaned of artifacts as previously described. The data analyst will examine each variable for outliers and distributional properties and flag and correct entry errors where possible

and will log-transform or otherwise normalize variables prior to analysis. From RedCap all datasets will then be securely stored using Box.com per the HRPP policy. They may need to be downloaded to University/AHC desktops for statistical analysis, however only a subset of the team will be given access to all files (study coordinator and PI) and the rest will have access to the de-identified files only. These laptops are password protected and maintained by the AHC. Although we do not anticipate many missing values in this short-term follow-up study, multiple imputation methods (e.g., Proc MI in SAS) will be used if missing data can reasonably be considered missing at random. Analyses will also be run without imputation and results compared. Analyses will be carried out using SAS version 9.4 (SAS Institute Inc.) using an intent-to-treat approach, with a 2tailed p<0.05 as the threshold for statistical significance. For Specific Aims 1, 2, and 3, body composition data, neurodevelopmental outcomes, and IGF-1 and IGFBP3 will be treated as continuously-distributed variables assessed at multiple time points. For the ERP outcomes (which are measured twice), the primary hypotheses will be addressed using a simple general linear regression model for term-equivalent measures, and another similar model for 4 month corrected age measures, with assigned group as the independent variable in both cases. For FFM (with up to 10 repeated measures) and IGF-1 models, mixed effects regression models (using

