PROC MIXED) will be used. The primary models will test assigned group (standard versus enhanced nutrition protocol) and assigned group x time interaction as the tests of differences in the group mean values for initial levels, and change over time, respectively, between intervention and control groups. To improve the precision of estimates, variables of interest (e.g., gestational age at birth, anthropometric z scores at birth, degree of illness, etc.) will be included in additional, secondary models. In addition, in Specific Aim 3, IGF-1 levels at both 1 week and 35 weeks will be examined as predictors of later neurodevelopment and body composition outcomes. IGF-1 will be considered a potential mediator of the intervention-outcome relationships if 1) the intervention is significantly associated with both IGF-1 levels and outcomes, 2) IGF-1 levels are significantly associated with FFM and neurodevelopmental outcomes, and 3) in a model that includes both IGF-1 and treatment group as predictors. the effect of treatment group on outcomes (mean differences) is diminished compared to results from models unadjusted for IGF-1. Other ways of assessing the possible role of IGF-1 in the treatment-outcome relationship will also be explored.

15.2 Power Analysis: A sample size of 40 infants in each treatment group (80 total) allows for up to a ~12% loss to follow-up after discharge and still have 35 infants per group. Our prior work showed a significant association of early nutrition (protein and calories in first week of life) with FFM gains throughout hospitalization (p<0.01 for both) in 34 VLBW preterm

> infants. We have also shown that higher energy (kcal/kg/day) across hospitalization was associated with faster speed of processing (shorter latency) in 16 preterm subjects. We therefore expect that this pilot study, which is 2-3 times as large as previous studies, will be sufficient to produce statistically significant differences between groups. As this is a pilot trial, however, we have not conducted a formal power calculation. Rather, the results of this pilot exploratory study will generate estimates of effect size that will then be used to calculate sample size for our planned larger trial.

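### Aim III can label IGF-1 a potential mediator without an arm-adjusted IGF-1/outcome test or any interval for the indirect effect; a cheap improvement to an exploratory analysis

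*Combined protocol and SAP*

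**What the plan says.** The rule is in Section 16.0, in the paragraph numbered 15.1 (Data Analysis Plan), and serves Specific Aim III. It has three conditions.

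1. "the intervention is significantly associated with both IGF-1 levels and outcomes".
2. "IGF-1 levels are significantly associated with FFM and neurodevelopmental outcomes".
3. In a model holding both IGF-1 and treatment group, "the effect of treatment group on outcomes (mean differences) is diminished compared to results from models unadjusted for IGF-1".

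Treatment group is first mentioned as a covariate in condition 3, and only the change in its own coefficient is used there. The IGF-1 coefficient from that model is not named as a test. No estimate or interval for an indirect effect appears anywhere. The plan adds that other approaches will be explored but names none.

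Three nearby statements bear on the point.
- On timing, "IGF-1 levels at both 1 week and 35 weeks will be examined as predictors of later neurodevelopment and body composition outcomes".
- On covariates, "variables of interest (e.g., gestational age at birth, anthropometric z scores at birth, degree of illness, etc.) will be included in additional, secondary models", with precision as the stated reason.
- On missing data, multiple imputation is planned where missing at random is reasonable, and "Analyses will also be run without imputation and results compared".

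**The concern.** If the intervention raises IGF-1 and also improves the outcome by another route, the two will correlate across the pooled arms even when IGF-1 has no effect. An IGF-1/outcome test without treatment group can be significant for that reason alone. Condition 3 is then the only remaining check, and it asks only for a reduction of any size.

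Confounding is a second route to the same error. IGF-1 is not randomised, and Section 2.1 says of the causes of growth failure that "many (e.g. illness and inflammation) of them remain largely out of our control". Illness could therefore plausibly affect both IGF-1 and growth within an arm.

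What is at stake is the use made of the label. Section 2.1 says that, if the mediation hypothesis is supported, "IGF-1 could then be used as a biomarker for prediction of later outcomes", and also as a tool for monitoring nutrition interventions. The pilot is meant to supply effect-size estimates for a larger trial, yet for mediation it commits to a label without an estimate.

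**Working it through.** **Inputs from the plan (Section 16.0).** Two-sided 0.05; 40 infants per arm, 35 after about 12% loss. Check: 40 × 0.88 = 35.2, and 5/40 = 12.5%, so the figure reproduces. No power, effect size or indirect-effect figure is stated.

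**Assumed inputs.** Path sizes in SD units: a = arm on IGF-1, b = IGF-1 on outcome given arm, c = direct effect of arm on outcome. The models are IGF-1 = a·arm + e1 and outcome = b·IGF-1 + c·arm + e2, with unit-variance errors. There is one IGF-1 value and one outcome measurement; FFM has up to 10 repeated measures, so its rates will differ. Each cell has 20,000 simulated trials.

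**Step 1: condition 2 without arm.** With b = 0, a = c and equal arms (arm variance 0.25), the induced correlation is 0.25a²/(1 + 0.25a²):
- a = 0.5: 0.0625/1.0625 = 0.06
- a = 0.7: 0.1225/1.1225 = 0.11
- a = 1.0: 0.25/1.25 = 0.20

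At 35 per arm the unadjusted test is significant in 7.7% of trials at 0.5 SD and 39.2% at 1.0 SD. Adjusted for arm it stays near 5%.

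**Step 2: condition 3.** In linear models on the same infants, the drop in the arm coefficient equals (estimated a) × (estimated b). With b = 0 the sign of the estimated b is a coin toss, so the arm effect is diminished in about half of trials (simulated 49.6%, 50.5%, 50.5%).

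**Step 3: full rule, inert IGF-1, no confounding** (35 per arm; 40 per arm in brackets).

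| a = c | condition 2 without arm | condition 2 with arm |
|---|---|---|
| 0.5 | 3.7% (4.4%) | 0.7% (0.9%) |
| 0.7 | 12.8% (14.4%) | 1.8% (1.9%) |
| 1.0 | 34.8% (37.4%) | 2.5% (2.5%) |

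**Step 4: the same with confounding** (b = 0, assumed residual IGF-1/outcome correlation 0.3, 35 per arm, a = c = 0.5/0.7/1.0). Without arm: 30/66/95%. With arm: 24/50/70%. With arm plus the confounder measured at an assumed reliability of 0.5: 12/23/30%; at 0.8: 4/7/10%. Arm adjustment alone does not solve this.

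**Step 5: an interval must not replace the rule.** Under the same confounding but with no treatment effect on the outcome (b = c = 0), the 95% bootstrap interval for the indirect effect, with no covariates, excludes zero in 40/56/71% of trials at a = 0.5/0.7/1.0. The three-part rule is met in about 2%, because it requires a significant total effect.

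**Step 6: cost in detection** (35 per arm, true mediation).

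| (a, b, c) | without arm | with arm | loss, points |
|---|---|---|---|
| (0.7, 0.4, 0) | 17.0% | 15.2% | 2 |
| (1, 0.7, 0) | 65.3% | 65.3% | 0 |
| (0.7, 0.4, 0.3) | 52% | 47% | about 5 |
| (0.7, 0.3, 0.4) | 53% | 39% | 14 |
| (0.7, 0.3, 0.5) | 63% | 46% | 17 |
| (1, 0.3, 0.5) | 84% | 59% | 25 |
| (0.7, 0.2, 0.7) | 60% | 28% | 31 |

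The last loss is computed before rounding. Where b is small and c is large, much of the loss is the arm-induced association of Step 1, not evidence of mediation.

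**Step 7: width.** For a = 0.7, b = 0.4 (true indirect effect 0.28 SD) the median bootstrap interval at 35 per arm is 0.05 to 0.55 SD.

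**The case against.** The strongest reply is that condition 2 is silent on treatment group, which is not the same as excluding it. The condition 3 model contains both terms, so the adjusted coefficient will exist, and an analyst may have meant it. That stands: the defect is an unspecified model, not a proven wrong one.

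The size is also conditional. At 0.5 SD without confounding the false-label rate is only 4%; 35% needs a 1.0 SD effect on both IGF-1 and the outcome. Condition 2 also names FFM and neurodevelopmental outcomes together. If all conditions must hold for two such outcomes, the unadjusted rates fall to 0.3/2.2/12.7% with independent outcome errors, or 0.5/3.7/16.3% with error correlation 0.3.

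Other parts are partly covered. Imputed datasets put the same infants in both models, so that issue is confined to the non-imputed run. The covariate models belong to a plan introduced for all three aims, so Aim III is not clearly left out; the gap is that they are not tied to the IGF-1/outcome model. Timing is already addressed by restricting IGF-1 to later outcomes.

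A reader might infer that requiring a significant total effect is itself an error, since it can miss real mediation. With (0.7, 0.4, 0) the rule is met in 17% of trials, against 73% for joint significance of the two paths. The documents do not support calling this an error. It is a defensible conservative gate, and Step 5 shows what it guards against. It does mean that a negative label says little when the total effect is small.

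**Conclusion.** The concern holds as a cheap improvement to an exploratory, secondary aim. Applied outcome by outcome with no arm term in condition 2, the rule labels an inert IGF-1 level in about 4/13/35% of trials at assumed arm effects of 0.5/0.7/1.0 SD, against about 1 to 2.5% with arm adjustment. Condition 3 adds little protection, and nothing in the plan shows how uncertain the indirect effect is.

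These rates rest on assumed effects, linear models and a single outcome measurement. A reader might infer that the trial will wrongly declare mediation a third of the time. The documents do not support that: they give no effect sizes, do not state that condition 2 is unadjusted, promise only a potential-mediator label, and leave room for other approaches. The primary outcome and safety are unaffected.

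**What to change.** - **(a)** Test condition 2 with the IGF-1 coefficient from the condition 3 model, which includes treatment group.
- **(b)** Whatever the label, report the indirect effect (arm effect on IGF-1 × arm-adjusted IGF-1 effect on outcome) with a bootstrap 95% CI beside the total effect, marked exploratory. In the non-imputed run, fit the models with and without IGF-1 on the same infants.
- **(c)** Include gestational age and birth z score in the IGF-1/outcome model. Add the day-of-life 1 SNAP only if it is scored before study nutrition starts, or else as a sensitivity analysis: Section 4.1 starts nutrition at IV access and Section 5.2 gives only the day of scoring, so the order is not shown. Use 35-week IGF-1 only for outcomes measured after it.
- **(d)** Keep the total-effect condition for the label, and do not declare mediation from the interval alone. IGF-1 is not randomised, and arm adjustment does not remove IGF-1/outcome confounding.

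The cost is plan wording and a short bootstrap program; every variable is already collected. The downsides are a wide interval and fewer positive labels under true mediation. In the cells examined, the loss is about 0 to 2 points under full mediation, about 5 points at (0.7, 0.4, 0.3), and 14 to 31 points where the IGF-1 effect is small (0.2 to 0.3) and the direct effect large (0.4 to 0.7).

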### 4.0 Study Intervention

4.1 Description: This nutritional intervention is designed to accelerate the addition of macronutrients over the first week of life to minimize the period of malnutrition, and is based upon the findings of numerous smaller, less comprehensive studies and expert opinion. Once consent is obtained, and the infant is admitted to the NICU, enrolled infants will be randomized to either receive parenteral nutrition per the standard NICU parenteral nutrition protocol or via the enhanced nutrition protocol for the first week of life via random envelope selection. Stratified

block randomization will be performed. Infants will be stratified by gestational age (22-25, 26-29, 30-32 weeks). Within each stratum, permuted block randomization will ensure that study personal are unable to predict treatment allocation. Infants

randomized to the enhanced nutrition protocol will receive starter total parenteral nutrition (TPN) initiated at 80 mls/kg/day to provide protein at 4 grams/kg/day and a glucose infusion rate (GIR) of ~5.5 mgs/kg/min as soon as IV access has been obtained. Enhanced nutrition protocol infants will also be started on intralipids (IL) at 2 grams/kg/day once IV access is obtained. Infants randomized to the enhanced nutrition protocol will receive 4 grams/kg/day of protein throughout the first week of life. IL will be increased to 3 grams/kg/day on day of life (DOL) 2 and to 3.5 grams/kg/day on DOL 3. They will remain on this amount for at least the first week of life or until sufficient enteral feeding volumes have been established. GIR will be advanced by  $\sim 1.5 \text{ mgs/kg/min per day}$ throughout the first week of life to a maximum of 12-14 mgs/kg/min. Again, they will then remain on this amount until sufficient enteral feedings have been established (typically approximately 1-2 weeks). Infants randomized to the standard nutrition protocol will receive macronutrients per the caregivers discretion, most commonly initiated with starter TPN at 60 mls/kg/day giving 3 grams/kg/day of protein and a GIR of ~4 and IL provided at 0-1 gram/kg/day. Advancement is most typically by 1

mg/kg/min per day for GIR and 1 gram/kg/day per day for IL and protein in the standard NICU protocol. Pertinent aspects of the differences in nutritional treatment in intervention and control groups are summarized in the table below

	Day 1	Day 2	Day 3	Day 4	Day 5	Day 6	Day 7	
Control								
GIR	4.2	5	6	7	8	9	10	

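### Does the pilot need a different sample-size justification because item 15.2 expects significant group differences without a power calculation?

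*Combined protocol and SAP*

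**What the plan says.** Item 15.2 (Power Analysis, within section 16.0 Data Management) sets 40 infants per group, so that 35 per group remain after about 12% loss following discharge. It then cites two earlier results from the same team. One links first-week protein and calories with fat-free mass (FFM) gains in 34 infants. The other found that "higher energy (kcal/kg/day) across hospitalization was associated with faster speed of processing (shorter latency) in 16 preterm subjects". From these, and because the pilot is said to be two to three times larger, the plan expects that it "will be sufficient to produce statistically significant differences between groups". The next sentence qualifies this: because the study is a pilot, "we have not conducted a formal power calculation". The paragraph closes by saying that the results will provide effect sizes for sizing a larger trial.

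Item 15.1 uses a "2tailed p<0.05 as the threshold for statistical significance". The event-related potential (ERP) outcomes are analysed by "a simple general linear regression model for term-equivalent measures" and a similar model at 4 months, with assigned group as the predictor. FFM and IGF-1 use mixed models. Under Aim 3, IGF-1 counts as a potential mediator if three conditions are met, the first being that "the intervention is significantly associated with both IGF-1 levels and outcomes"; the rule ends with "Other ways of assessing the possible role of IGF-1 in the treatment-outcome relationship will also be explored".

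Section 3.1 makes first-week calorie and protein intake the primary outcome. Growth, neurodevelopment and growth factors are secondary (section 3.2).

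**The concern.** A prediction of significance under a power heading reads as a claim that the trial is adequately powered, and the premises do not support it.

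- **Type of evidence.** Sections 2.2 and 2.3 describe the earlier work as observational. A significant slope on naturally varying intake does not give the mean difference between randomised arms. That difference depends on the intake contrast achieved, the outcome SD and any confounding in the earlier cohort.
- **Exposure.** The study of 16 infants concerned energy over the whole hospital stay. Here infants are allocated to the "enhanced nutrition protocol for the first week of life via random envelope selection", with the amounts reached then held until enteral feeding is established.
- **Contrast.** Section 14.1 treats it as an open question whether intolerance will shrink the difference in intake between the arms.
- **Size.** Being larger than an earlier study gives no power figure.

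At stake is interpretation. If readers have been told that the sample suffices, a non-significant ERP or IGF-1 result could be taken as evidence of no effect. Two of the three mediation conditions are also worded in terms of significance.

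**Working it through.** **1. The plan's own arithmetic.** 40 × (1 − 0.12) = 35.2, and 35 / 0.88 = 39.8, which rounds up to 40. The step from 40 to 35 per group reproduces. Section 24.1 reports about 85% return in an earlier cohort: 40 × 0.85 = 34. Item 15.2 states no power, effect size, SD or target, so there is no power figure to reproduce.

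**2. The size ratio.** 80 / 34 = 2.4, which fits the stated two to three times. 80 / 16 = 5.0, which does not; for that study the plan understates its own argument. Neither ratio bears on power without an effect size.

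**3. Power for a simple two-group comparison.** This matches the ERP models. Inputs: two-sided 0.05 (item 15.1) and equal groups of n complete cases. The standardised differences d are assumed, because the documents give none. Power comes from the noncentral t distribution with 2n − 2 degrees of freedom and noncentrality d × √(n/2). The 95% CI half-width in SD units is t(0.975, 2n − 2) × √(2/n); at n = 35 it is 1.995 × √(2/35) = 0.477.

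| n per group | d for 80% power | Power at d = 0.3 | d = 0.5 | d = 0.8 | CI half-width |
|---|---|---|---|---|---|
| 35 | 0.679 | 23.6% | 54.1% | 91.0% | 0.477 SD |
| 34 | 0.690 | 23.0% | 52.9% | 90.2% | 0.484 SD |

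**4. What the earlier FFM result could imply.** At n = 34, p = 0.01 corresponds to t = 2.738 on 32 degrees of freedom. For a simple correlation, r = t / √(t² + 32) = 2.738 / √(7.50 + 32) = 0.44. Let c be the between-arm difference in intake, in SDs of intake in the earlier cohort. The documents do not give c, so it is assumed. Then d = r × c / √(1 − r²), and at 35 per group:

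| c | d | Power |
|---|---|---|
| 0.5 | 0.24 | 17% |
| 1 | 0.48 | 51% |
| 1.5 | 0.73 | 85% |
| 2 | 0.97 | 98% |

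This treats the FFM outcome as a single two-group comparison and the observational slope as causal. It shows only that the cited result is compatible with anything from low to very high power. The planned FFM and IGF-1 mixed models could be more or less precise, depending on within-infant correlations that are not given.

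**5. How firm these figures are.** They can move either way.

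- The 12% covers loss after discharge only. Earlier deaths or withdrawals, and ERP recordings unusable after artifact cleaning, would come on top. At an assumed 30 or 28 per group, 80% power needs 0.74 or 0.76 SD, and power at 0.5 SD is 48% or 45%.
- Item 15.1 also plans covariate-adjusted secondary models. If covariates explain an assumed 20% or 30% of outcome variance, the detectable difference at 35 per group is about 0.679 × √0.8 = 0.61 SD or 0.679 × √0.7 = 0.57 SD.

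**6. What depends on the sentence.** The number 80 is tied to retention (item 15.2) and accrual (section 24.1), not to the expectation of significance. The models, the significance threshold and the mediation rule in item 15.1 are all stated without reference to it. Removing it would alter none of them.

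**The case for a change.** The strongest case for a change is that the disclaimer does not withdraw the expectation. The paragraph predicts significance and then says that power was never calculated, and these statements sit badly together. A reader who remembers the first will be less cautious with a null secondary result, although power for a 0.5 SD ERP difference would be only about 53–54%. Deleting one sentence and adding a detectable difference would cost no infants, visits or models.

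Most of the logic stands: the inference is weak and the sentence would be better softened. What does not stand is the harm. Nowhere does the plan say that a non-significant result will be read as no effect. The mediation rule says when IGF-1 will be considered a potential mediator; it does not exclude mediation otherwise, and it leaves other methods open. An inserted power statement would also bring its own difficulty. Figures at 34–35 per group are a best case for retention and are unadjusted, as step 5 of the working shows, so they would put doubtful precision into a pilot that makes no numerical power claim.

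**Conclusion.** The sentence overstates what the earlier studies support, but the plan needs no change. At 35 per group a two-group ERP comparison has 80% power for about 0.68 SD. Over assumed differences of 0.3 to 0.8 SD, at 34–35 per group, power runs from about 23% to 91%. The expectation is therefore unestablished rather than contradicted. The figures assume complete cases, equal groups, no covariate adjustment and effect sizes chosen for illustration.

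The primary feasibility outcome is untouched, because the sentence rests on FFM and speed of processing, which are secondary. The paragraph already says that the study is a pilot, that no formal calculation was made and that estimating effect sizes is the aim. Analysts following it would report estimates with confidence intervals from the models already planned. The mismatch between two to three times and the fivefold ratio for the study of 16 infants is a clerical slip with no consequence. Softening the sentence is an editorial choice.
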